Details on the previous experience with tetrabenazine in patients with Huntington disease can be found in the SD-809 ER Investigator's Brochure (IB), which includes the tetrabenazine prescribing information.

Limitations of the Current Commercial Product

The commercial form of tetrabenazine (Xenazine[®], Nitoman[®]) is an immediate release formulation. While generally effective in the treatment of chorea, tetrabenazine has limitations for use in Huntington disease patients, including:

- High peak concentrations of the active metabolites. Clinical experience in patients, and Phase 1 data in healthy volunteers, indicate that important adverse events of tetrabenazine, such as somnolence, akathisia, and anxiety are often associated with peak concentration after dosing.

- Short half-lives of the active metabolites and the attendant requirement to dose the immediate release formulation frequently. The rapid decline in plasma concentrations may lead to loss of efficacy at the end of the dosing interval. The fluctuation in plasma concentration, as indicated by high peak concentrations and low trough concentrations, necessitates more frequent dosing. Therefore, many patients must take tetrabenazine three times a day due to the short half-lives of the active metabolites, α -HTBZ and β -HTBZ. A less frequent dosing schedule is preferred as it may improve medication compliance.
- The active metabolites α - and β -HTBZ are either primarily (α) or exclusively (β) metabolized by CYP2D6. Polymorphisms in the CYP2D6 gene necessitate genotyping to prevent poor metabolizers from significantly greater exposure to the active drug moiety than extensive metabolizers.

To address the limitations of commercial tetrabenazine, Auspex has developed a deuterated analogue of tetrabenazine (referred to as SD-809) which, due to the deuteration, is eliminated more slowly than tetrabenazine (See below). It is also administered in an extended release formulation. As outlined in Section 1.4 and the Investigator's Brochure, SD-809 extended release (ER) has been shown to reduce plasma fluctuation and dosing frequency and thus, has the potential to improve overall tolerability as compared to tetrabenazine.

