2 STUDY OBJECTIVES

The objectives of this study are:

1. Evaluate the safety and tolerability of titration and maintenance therapy with SD-809 ER
2. Evaluate the safety and tolerability of switching subjects from tetrabenazine to SD-809 ER
3. Evaluate the pharmacokinetics of tetrabenazine, SD-809 and their respective α - and β -HTBZ metabolites in subjects switching from tetrabenazine to SD-809 ER

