3.2 *Rationale for Study Design*

The study is designed to evaluate the long term safety and tolerability of SD-809 ER in subjects with chorea associated with HD. Two cohorts of subjects may enter the study: 1) Rollover subjects, who successfully complete the well-controlled efficacy study (SD-809-C-15) and 2) Switch subjects, who are receiving FDA-approved doses of tetrabenazine for treatment of chorea.

Given the two groups of subjects entering this trial have different background therapy at entry; identification of their optimal dose will be approached differently. Rollover subjects from Study SD-809-C-15 will have discontinued study medication (SD-809 ER or placebo) for at least one week and consequently they will begin dosing at 6 mg/day and titrate to their optimal dose level for up to 8 weeks. In contrast, Switch subjects will be on a stable dose of TBZ at entry and will make a direct conversion to SD-809 ER overnight based on their incoming TBZ regimen. As such, Switch subjects should reach their target dose more rapidly and they are allowed up to 4 weeks to adjust their SD-809 ER regimen after conversion. Although the time to reach an optimal dose may differ between these cohorts, both groups are expected to reach a pharmacologically active dose by two weeks: Rollover subjects would be at 12 mg/day, unless they experienced adverse events or adequate chorea control; and Switch subjects would have converted to a dose level that provides comparable exposure to their incoming tetrabenazine dose, with one intervening visit to evaluate/adjust dose level. Accordingly, the long term period of the study will be deemed to have started after two weeks of treatment even though dose adjustment may continue after this point.

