4.2 Inclusion Criteria

1. Subject is at least 18 years of age or the age of majority (whichever is older) at Screening.

¹ The maximum dose of tetrabenazine is 100 mg/day (with a maximum single dose of 37.5 mg), unless the subject has known impaired CYP2D6 function, in which case the maximum dose is 50 mg/day with a maximum single dose of 25 mg.

2. Subject has been diagnosed with manifest HD, as indicated by characteristic motor exam features, and has a documented expanded CAG repeat (≥ 37) at or before Screening¹.
3. Subject meets either of the following:
 - Has successfully completed² participation in Study SD-809-C-15 OR
 - Has been receiving an FDA approved dose of tetrabenazine³ that has been stable for ≥ 8 weeks before Screening and is providing a therapeutic benefit for control of chorea
4. Subject has a Total Functional Capacity (TFC) score ≥ 5 at Screening.
5. Subject is able to swallow study medication whole.
6. Subject has provided written, informed consent or, if subject lacks the capacity to provide informed consent (as determined by an independent assessment by a qualified healthcare provider not directly involved in other study activities), a legally authorized representative (LAR) has provided written informed consent and the subject has provided assent.
7. Subject has provided a Research Advance Directive if subject has the capacity to provide informed consent (See Section 6.12).
8. Female subjects of childbearing potential⁴ agree to use an acceptable method of contraception from screening through study completion. Female subjects of childbearing potential must be using one of the following acceptable birth control methods if sexually active:
 - IUD or intrauterine system in place for at least 3 months prior to screening;
 - Subject or partner using barrier method (e.g., condom, diaphragm, or cervical cap) with spermicide from screening through study completion;
 - Partner has a documented vasectomy > 6 months prior to Baseline.

¹ A CAG repeat number obtained prior to the Screening Visit may be used to document subject eligibility if either of the following conditions are met:

- At Screening, there is documentation available in the subject's records that shows the subject has an expanded CAG repeat (≥ 37) from a prior laboratory assessment.

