9.9.1 Adverse Events

Adverse events will be coded using version 16.1 of the Medical Dictionary for Regulatory Activities (MedDRA); the MedDRA version will be noted in the CSR. Treatment-emergent AEs (TEAEs) are events that 1) begin after treatment with study drug in the current study and that are not present at baseline or 2) if present at baseline, have worsened in severity. For AEs with missing start dates, the AE will be considered treatment-emergent unless there is additional information indicating that the AE started prior to the first treatment. All analyses of TEAEs will be performed separately for TEAEs that occurred during the titration period (for Rollover subjects only), during the dose-adjustment period (for Switch subjects only), during the extended dose-adjustment period (for Switch subjects only), during the stable dose period, and during the entire treatment period. To be conservative, all adverse events that occurred during the follow-up period will be counted as events that occurred during the last available treatment period. In order to be included in the analysis for a given time period, a subjects must have at least one visit during the time period.

For the Switch cohort, an overview of AEs occurring during the Screening period will present the number and percentage of subjects in the following categories:

- Any AEs
- Any serious AEs (SAEs)
- Any severe AEs
- Any AE(s) leading to death

An overview of TEAEs will present the number and percentage of subjects in the following categories:

- Any TEAEs
- Any serious TEAEs

-
- Any severe TEAEs
 - Any treatment-related TEAEs
 - Any TEAEs resulting in dose reduction
 - Any TEAEs resulting in dose suspension
 - Any TEAEs resulting in withdrawal from the study
 - Any treatment-related TEAEs resulting in withdrawal from the study
 - Any TEAEs resulting in dose reduction, dose suspension, or withdrawal from the study
 - Any TEAE(s) leading to death

TEAEs, serious TEAEs, TEAEs that led to dose reduction, TEAEs that led to dose suspension, TEAEs that led to withdrawal from the study, TEAEs that occurred in at least 4% of Rollover or Switch cohort subjects in the Safety Population across all time periods, will be summarized at the subject level by MedDRA system organ class (SOC) and preferred term using frequencies and percentages.

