Exposure adjusted incidence rates (number of patients with an event per person-year) will also be presented for the above TEAE overview categories, all preferred terms, and selected AEs of interest by patient cohort and study (First Active in C15, First Placebo in C15, Rollover in C16, and Switch in C16). AEs of agitation, somnolence, insomnia, anxiety and fall will be defined as events with matched preferred terms. In addition, AEs with selected preferred terms will be combined into the AEs of interest as follows:

- Akathisia and Restlessness: Akathisia, Hyperkinesia, Psychomotor hyperactivity, Restlessness, Agitation
- Dysphagia: Aphagia, Dysphagia
- Parkinsonism: Akinesia, Bradykinesia, Cogwheel rigidity, Freezing phenomenon, Hypertonia, Masked facies, Muscle rigidity, On and off phenomenon', Parkinsonian crisis, Parkinsonian gait, Parkinsonian rest tremor, Parkinsonism, Parkinson's disease, Resting tremor
- Suicidality: Completed suicide, Depression suicidal, Intentional overdose, Intentional self-injury, Poisoning deliberate, Self-injurious ideation, Suicidal behavior, Suicidal ideation, Suicide attempt.
- Depression: all preferred terms containing “depression”

Incidence rate will be calculated as:

Number of patients with given event/ Person-years for the event

Person-years for a selected event are defined as the sum of exposure days across all subjects divided by 365.25. Subjects with an event of the given type contribute days from the date of their first treatment dose until the date of the first event of the given type. Subjects without an event of the given type contribute days from date of their first treatment dose until their treatment end date. Events that occurred after the last dose date of each study period were not included.

TEAEs and treatment-related TEAEs, categorized by system organ class, preferred term, and maximum severity (mild, moderate, or severe), will be summarized by study period using counts and percentages. In addition, TEAEs, categorized by system organ class, preferred term, and relationship to study drug (unrelated, related), will be summarized by study period using counts and percentages. TEAEs that are classified as possibly, probably, or definitely related to study drug on the AE eCRF, or for which the relationship to study drug is missing, will be considered treatment related. Unrelated AEs include those classified as unrelated or unlikely related on the AE eCRF.

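### In the exposure-adjusted AE table (SAP 9.9.1), the Switch column counts only what is new or worse than on tetrabenazine, yet stands unlabelled beside columns with an off-drug baseline or from C-15

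*Protocol*

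**What the plan says.** **Entry state.** Protocol 3.2 opens its dosing rationale with "Given the two groups of subjects entering this trial have different background therapy at entry". It goes on: "Switch subjects will be on a stable dose of TBZ at entry and will make a direct conversion to SD-809 ER overnight". Inclusion criterion 3 (Protocol 4.2) requires a tetrabenazine dose stable for at least "8 weeks before Screening and is providing a therapeutic benefit for control of chorea". Rollover subjects have been off SD-809 or placebo for at least a week and restart at the lowest dose. SAP 8.7 follows this. The Switch baseline is the last value before the first SD-809 dose. For assessments scheduled at C-15 Week 13 or C-16 Baseline, the Rollover baseline is an off-treatment value, at least 4 days after the last dose.

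**What counts.** SAP 9.9.1 counts as treatment-emergent those events that begin after study drug in this study and "are not present at baseline or 2) if present at baseline, have worsened in severity". The rule is the same for both cohorts.

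**The rate.** It is the number of subjects with the event divided by person-years. "Subjects without an event of the given type contribute days from date of their first treatment dose until their treatment end date". Rates are planned for the overview categories, all preferred terms and the AEs of interest, in four columns: "First Active in C15, First Placebo in C15, Rollover in C16, and Switch in C16". The SAP attaches no caveat to the Switch column.

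**Objective 2** (Protocol 2): "Evaluate the safety and tolerability of switching subjects from tetrabenazine to SD-809 ER".

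**The concern.** Protocol 1.2 states that "important adverse events of tetrabenazine, such as somnolence, akathisia, and anxiety are often associated with peak concentration after dosing", and Protocol 1.4 describes SD-809 adverse events as qualitatively similar to those of tetrabenazine. All three effects feed the SAP's AEs of interest. Somnolence that appears in a Rollover subject during titration is new and is counted. The same somnolence in a Switch subject, present on tetrabenazine and continuing at the same severity, is never counted, and the subject's whole treatment time goes into the denominator as event-free.

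The Switch column therefore answers a different question from its neighbours, and nothing in the table says so. A reader setting Switch against Rollover or C-15 placebo would be comparing different quantities.

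**Working it through.** The plan states no figure on this point: there is no formal testing (SAP 8.1), the sample size is not statistical (SAP 8.2), and no prevalence of tetrabenazine effects at Switch entry is given. The sizes below are illustrations under stated assumptions.

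**1. Dilution of the Switch rate against its own at-risk rate.** Let *p* be the share of Switch subjects with the event ongoing and unchanged at Baseline, *L* the new-onset rate per year among the rest, and *T* the years on treatment. The SAP formula then gives

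reported rate = (1−p)(1−e^(−LT)) / [ (1−p)(1−e^(−LT))/L + pT ].

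- p = 0.1, L = 0.1, T = 1: numerator 0.9 × 0.0952 = 0.0856; denominator 0.856 + 0.1 = 0.956; rate 0.0895; ratio to L = 0.90.
- p = 0.3, L = 0.5, T = 3: numerator 0.7 × 0.777 = 0.544; denominator 1.088 + 0.9 = 1.988; rate 0.274; ratio to L = 0.55.

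Over p = 0.1–0.3, L = 0.1–0.5 and T = 1–3 the ratio runs from 0.55 to 0.90. With L held at 0.1 it runs from about 0.67 to 0.90.

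**2. Switch against Rollover when the true burden is equal.** Assume 36 Switch and 80 Rollover subjects (the planned numbers) and the same share *s* affected on drug in both cohorts. A fraction *f* of affected Switch subjects already has the effect, unchanged, at entry. New onset is at day 28, with 2 years on treatment. Take s = 20%.

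Rollover: 16 / (16 × 28/365.25 + 64 × 2) = 16/129.2 = 12.4 per 100 person-years.

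| f | Switch TEAE % | Switch rate per 100 PY | Switch/Rollover, SAP rule | Switch/Rollover, at-risk subjects only |
|---|---|---|---|---|
| 25% | 15.0 | 8.8 | 0.71 | 0.75 |
| 50% | 10.0 | 5.5 | 0.45 | 0.50 |
| 75% | 5.0 | 2.6 | 0.21 | 0.25 |

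For f = 50%: 3.6 / (3.6 × 28/365.25 + 32.4 × 2) = 3.6/65.1 = 5.5. Over s = 10–30% and 1–3 years, the SAP-rule ratio is 0.68–0.73, 0.41–0.48 and 0.19–0.23 for the three values of f.

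The last column matters for the fix. Removing subjects with a baseline event corrects the person-time, but most of the gap comes from carried-over events missing from the numerator.

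**3. What other outputs show.**

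- The Switch Screening-period AE overview (SAP 9.9.1) has four broad categories and no preferred terms.
- Adverse findings at the Screening visit go to the Medical History form (Protocol 7.2.1). SAP 9.3 summarises these by preferred term, without later status.
- Pre-existing conditions that do not worsen, and improvements in past conditions, are not AEs (Protocol 7.1.1).
- SAP 9.9.7 gives by-visit observed values and changes from baseline for ESS, BARS, HADS, SDQ, UPDRS speech and others.

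**The case against.** **The on-tetrabenazine baseline is the right one for Objective 2.** What is new or worse after the switch is a natural question for a switching study, and new-or-worsened is the usual TEAE convention. This stands. The difficulty is the unlabelled juxtaposition with columns that have another baseline.

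**The rating scales already show persistence and improvement.** Largely true. Observed ESS or BARS scores show sleepiness or akathisia on SD-809 whenever it began, and a fall from baseline shows improvement. A reader might infer that carried-over burden and resolution after switching are invisible; SAP 9.9.7 does not support that. But the scales do not enter the AE rates, and none is specified for insomnia or falls, both AEs of interest.

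**Effects may not carry over unchanged.** Protocol 3.2 expects comparable AUC with reduced peaks, and the quoted sentence in Protocol 1.2 ties these effects to peaks. The HADS depression, SDQ and dysarthria exclusions also limit some effects at entry. This stands, and it is a reason not to assert a size.

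**The placebo comparison is narrower than it may appear.** A reader might infer that all Switch TEAE tables sit beside placebo. Only the exposure-adjusted table has C-15 columns; ordinary TEAE counts are summarised by C-16 cohort (SAP 8.7). The C-16 Rollover column is also on SD-809; only its baseline is off drug. The SAP plans no formal Switch-versus-placebo comparison.

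**Conclusion.** The point holds for the exposure-adjusted table in SAP 9.9.1. One rule applied to different entry states omits unchanged tetrabenazine effects from the Switch numerator and keeps those subjects' time in the denominator. Switch rates are expected to be low relative to the other columns.

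The direction follows from the text; the size does not. The 0.55–0.90 range assumes 10–30% carry-over. Its lower end needs an onset rate of 0.5 per year for 3 years, which is about 78% cumulative incidence (1 − e^(−1.5)). The ratios of about 0.7, 0.45 and 0.2 assume equal true burden and an assumed share already affected at entry.

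Two stronger readings are tempting. One is that Switch will look better tolerated than placebo; that is a prediction the documents cannot confirm. The other is that the rates are biased by a known 10–45%; that range is only the illustration above. This is a cheap improvement to a descriptive table. It does not call the design or the Objective 2 baseline into question.

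**What to change.** In SAP 9.9.1:

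1. For each preferred term and AE of interest, compute the rate in all four columns among subjects without that event ongoing at Baseline (from the AE and Medical History forms), in both numerator and person-years. Put worsened baseline events on a separate line. This corrects the denominator only.
2. Head or footnote the Switch column: *new or worsened relative to tetrabenazine; not directly comparable with Rollover or C-15 columns*. Item 1 does not remove the need for this label.
3. For Switch, show the number of subjects with each AE of interest ongoing at Baseline beside the TEAE count. Give later status only for events on the AE form, and show *status not recorded* for Medical History items. Cross-refer to the observed ESS, BARS, HADS and SDQ values.

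The cost is SAP wording and one small table from data already collected, with no change to visits, treatment or eligibility. Switch rates become somewhat less favourable. Baseline status will be incomplete: Switch medical history is taken at Screening only, and nothing requires its items to be followed afterwards, so a full resolved/unchanged/worsened table cannot be promised.

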3.3 Rationale for Dose Selection

As with tetrabenazine, SD-809 ER treatment will be individualized, and, therefore fixed doses will not be evaluated in the study. The starting dose of 6 mg of SD-809 ER provides an AUC of total ($\alpha+\beta$)-HTBZ that is comparable to the 12.5 mg starting dose of tetrabenazine, but with a lower peak concentration and higher trough concentration. The dose level of SD-809 ER treatment will be evaluated on a weekly basis during the titration/dose adjustment period, based on assessments of chorea control and adverse events, in order to determine if dose adjustment is needed. This approach is consistent with the tetrabenazine prescribing information.

Dose adjustments should occur in increments of 6 mg/day (each week) (6 mg/day or 12 mg/day after a total daily dose of 48 mg is reached). Dose reductions in increments greater than 6 mg should be reviewed with the Clinical Monitor (See Section 5.2.5).

The maximum total daily dose of SD-809 ER is 72 mg per day, unless the subject is receiving a strong CYP2D6 inhibitor (e.g., paroxetine, See Appendix 11), in which case the maximum total daily dose is 42 mg.

4 STUDY POPULATION

4.1 Population Characteristics

Male and female adult subjects with HD who are receiving approved doses of tetrabenazine¹ for treatment of chorea or have successfully completed the SD-809-C-15 efficacy study and meet eligibility criteria will be enrolled.

4.2 Inclusion Criteria

1. Subject is at least 18 years of age or the age of majority (whichever is older) at Screening.

¹ The maximum dose of tetrabenazine is 100 mg/day (with a maximum single dose of 37.5 mg), unless the subject has known impaired CYP2D6 function, in which case the maximum dose is 50 mg/day with a maximum single dose of 25 mg.

2. Subject has been diagnosed with manifest HD, as indicated by characteristic motor exam features, and has a documented expanded CAG repeat (≥ 37) at or before Screening¹.
3. Subject meets either of the following:
 - Has successfully completed² participation in Study SD-809-C-15 OR
 - Has been receiving an FDA approved dose of tetrabenazine³ that has been stable for ≥ 8 weeks before Screening and is providing a therapeutic benefit for control of chorea
4. Subject has a Total Functional Capacity (TFC) score ≥ 5 at Screening.
5. Subject is able to swallow study medication whole.
6. Subject has provided written, informed consent or, if subject lacks the capacity to provide informed consent (as determined by an independent assessment by a qualified healthcare provider not directly involved in other study activities), a legally authorized representative (LAR) has provided written informed consent and the subject has provided assent.
7. Subject has provided a Research Advance Directive if subject has the capacity to provide informed consent (See Section 6.12).
8. Female subjects of childbearing potential⁴ agree to use an acceptable method of contraception from screening through study completion. Female subjects of childbearing potential must be using one of the following acceptable birth control methods if sexually active:
 - IUD or intrauterine system in place for at least 3 months prior to screening;
 - Subject or partner using barrier method (e.g., condom, diaphragm, or cervical cap) with spermicide from screening through study completion;
 - Partner has a documented vasectomy > 6 months prior to Baseline.

¹ A CAG repeat number obtained prior to the Screening Visit may be used to document subject eligibility if either of the following conditions are met:

- At Screening, there is documentation available in the subject's records that shows the subject has an expanded CAG repeat (≥ 37) from a prior laboratory assessment.
- At Screening, there is documentation available of a subject's prior laboratory assessment of an allele length that states a subject has a genotype consistent with a diagnosis of HD (i.e., laboratory analysis confirming the CAG repeat number was at least 40).

Note: If neither condition above is met, results from the CAG repeat sample collected at the Screening Visit must be used to determine study eligibility. A CAG Repeat Number of ≥ 37 must be documented prior to enrolling a subject into the study.

Note: Regardless of whether a prior CAG result is available, all Switch subjects will undergo CAG repeat testing at the Screening Visit, and any enrolled subject whose CAG repeat is found not to be ≥ 37 will be withdrawn from the study.

² Successful completion of Study SD-809-C-15 is defined as (1) study participation through Week 13 (2) the subject has generally been compliant with study medication and procedures, in the opinion of the investigator and (3) the subject has no ongoing adverse events that are serious (SAE) or severe in intensity or are expected to interfere with safety evaluations in this study.

³ The maximum dose of tetrabenazine is 100 mg/day (with a maximum single dose of 37.5 mg), unless the subject has known impaired CYP2D6 function, in which case the maximum dose is 50 mg/day with a maximum single dose of 25 mg.

⁴ Non-childbearing potential for females is defined as postmenopausal (amenorrheic for at least 1 year and serum follicle stimulating hormone (FSH) level consistent with postmenopausal status), or a documented hysterectomy; bilateral oophorectomy; or bilateral tubal ligation ≥ 6 months prior to study initiation.

- Stable hormonal contraception (with approved oral, transdermal, or depot regimen) for at least 3 months prior to screening.
9. The subject has a reliable caregiver who interacts with the patient on a daily basis, oversees study drug administration, assures attendance at study visits and participates in evaluations, as required.
 - Note: Subjects with a TFC score of 5-7 at Screening must have a live-in caregiver
 - Note: Subjects with a TFC score of 5-7 at Screening or those who enrolled with the consent of an LAR, must have caregivers present at all study visits.
 - Note: For subjects with a TFC score of 8-13 at Screening who did not require an LAR to provide informed consent, the caregiver must attend the following visits: Screening, Baseline, Weeks 4, 8, 15, 28 and visits every 13 weeks thereafter through the End of Treatment visit. Caregivers will be encouraged to attend other visits.
 10. Subject is able to ambulate without assistance for at least 20 yards (Note: The use of assistive devices (i.e., walker, cane) are permitted during ambulation).
 11. Has sufficient reading skills to comprehend the subject completed rating scales.

4.3 *Exclusion Criteria*

Subjects meeting any of the following criteria will be excluded:

1. Subject has a serious untreated or undertreated psychiatric illness, such as depression, at Screening or Baseline.
 - Note: Subjects receiving antidepressant therapy may be enrolled if on a stable dose for at least 8 weeks before Screening (See Appendix 12) for prohibited antidepressants).
2. Subject has active suicidal ideation at Screening or Baseline.
3. Subject has history of any of the following suicidal thoughts or behavior at Screening or Baseline:
 - Previous intent to act on suicidal ideation with a specific plan (positive answer to question 5 on C-SSRS), irrespective of level of ambivalence at the time of suicidal thought
 - Previous preparatory acts or behavior
 - A previous actual, interrupted or aborted suicide attempt
4. Subject has a score ≥ 11 on the depression subscale of the Hospital Anxiety and Depression Scale (HADS) at Baseline.
5. Subject has an unstable or serious medical or psychiatric illness at Screening or Baseline.
6. Subject has received tetrabenazine within 7 days of Baseline (Rollover subjects).
7. Subject has received any of the following concomitant medications within 30 days of Screening or Baseline:
 - Antipsychotics (See [Appendix 13](#))
 - Metoclopramide
 - Monoamine oxidase inhibitors (MAOI)
 - Levodopa or dopamine agonists

- Reserpine
 - Amantadine
 - Memantine (Rollover subjects only)
 - Switch subjects may receive Memantine if on a stable, approved dose for at least 30 days.
8. Subject has a score of ≥ 11 on the Swallowing Disturbance Questionnaire (SDQ) at Screening or Baseline.
9. Subject has a Unified Parkinson's Disease Rating Scale (UPDRS) dysarthria score of ≥ 3 at Screening or Baseline.
10. Subject requires treatment with drugs known to prolong the QT interval. Note:
- Quetiapine (Seroquel) is not allowed.
 - Escitalopram (Lexapro or Cipralex)¹ is allowed when administered according to approved labeling.
 - Citalopram (Celexa)² is allowed when administered according to approved labeling.
 - See [Appendix 16](#) for Celexa and Lexapro (Cipralex) dosing information
 - See Appendix 12 for a complete list of prohibited or restricted QT prolonging drugs.
11. Subject has a QTcF value >450 ms (males) or >460 ms (females), or >480 ms (with right bundle branch block) on 12-lead ECG at Screening.
- Note: Subjects with left bundle branch block are not eligible.
12. Subject has evidence of hepatic impairment at Screening, as indicated by:
- AST or ALT >2.5 times the upper limit of normal.
 - Alkaline phosphatase (ALP) or total bilirubin (TBil) >2 times the upper limit of normal (ULN)
 - Note: Subjects with Gilbert's Syndrome are eligible to participate if approved by the Clinical Monitor.
 - Note: Subjects with abnormalities in two or more of these analytes (AST, ALT, ALP, TBil) must be approved by the Clinical Monitor in order to be enrolled.
 - Prothrombin time > 4 sec prolonged.
 - Positive Hepatitis B surface antigen (HBsAg).
13. Subject has evidence of significant renal impairment at Screening, indicated by a creatinine clearance <50 mL/min, as estimated by the Cockcroft-Gault formula.
14. Subject has known allergy to any of the components of study medication.
15. Subject has participated in an investigational drug or device trial other than SD-809-C-15 within 30 days (or 5 drug half-lives) of Screening, whichever is longer.

¹ Escitalopram (Lexapro or Cipralex): The maximum allowed dose is 20 mg/day. The maximum dose for subjects ≥ 65 years old is 10 mg/day.

² Citalopram (Celexa) is allowed with the following restrictions (See Appendix 16):

- d) If the subject is a known CYP2C19 poor metabolizer, Celexa is not allowed.
- e) If the subject is > 60 years old or is receiving cimetidine, omeprazole, esomeprazole, fluconazole, fluoxetine or ticlopidine, the maximum allowed dose is 20 mg/day.
- f) If the subject is ≤ 60 years old and is not receiving any of the medications in (b) above, the maximum allowed dose is 40 mg.

16. Subject is pregnant or breast-feeding at Screening or Baseline.
17. Subject acknowledges present use of illicit drugs at Screening or Baseline.
18. Subject has a history of alcohol or substance abuse in the previous 12 months, as defined in the DSM-IV (See Operations Manual), or subject is unable to refrain from substance abuse throughout the study.

